8.9.3 SENSITIVITY ANALYSES

Sensitivity Analysis

1. The primary analysis will be repeated based on all reported MS relapses (rather than just confirmed ones).
2. A time to relapses analysis using Cox proportional hazards model with first IRAP-confirmed relapse as the primary event will be conducted to compare with the primary analysis in a negative binomial model. The Cox proportional hazards model will be specified with treatment, region, number of relapses in previous year, baseline EDSS score, baseline number of T1 Gd-enhancing lesions sex and the subject's age at baseline as covariates.
3. To assess the effects of treatment withdrawals, the primary analysis will be repeated using the information on relapses which occur during the period following drug withdrawal to the end of the study period regardless of whether additional treatment were utilized. Relapses which occurred after permanent discontinuation of study medication will be included and natural log (time on study in years) rather than the natural log (time on study drug in years) will be used as the offset variable in the negative binomial model, which is the primary analysis.
4. We will examine the dropouts from the trial using all participants who provided withdrawal of consent excluding deaths. Multiple imputation will be used to impute the expected number of relapses a participant would have had if they had continued to participate in the trial. To perform the imputation, 10 replicates will be used since a relapse on treatment is relatively low frequency event. The covariates used to model and predict the imputations will include: treatment, region, number of relapses in previous year, baseline EDSS score, baseline number of T1 Gd-enhancing lesions sex and the subject's age at baseline as covariates.
5. For secondary outcomes T1 Gd enhancing, T2 NELs, and 12 week CDP, the effects of dropouts and study discontinuations will be similarly evaluated as number 4 above.
6. Additional sensitivity analyses may be defined in the analysis plan prior to database lock.

8.9.4 TERTIARY EFFICACY AND OTHER VARIABLES

All tertiary analyses will be assessed at a Type I error of 0.05 with no adjustment for multiplicity.

1. Change in MSFC score from baseline to Week 96
2. Time to Confirmed Disability Progression (CDP) for at least 24 weeks
3. Time to Confirmed Disability Improvement (CDI) for at least 12 weeks
4. Time to Confirmed Disability Improvement (CDI) for at least 24 weeks
5. Health outcomes (MSQoL-54 (inclusive of SF36); FIS, hospitalization, steroid use, time out of work)
6. Total volume of Gd enhancing T1 lesions per MRI scan over the treatment period
7. Volume of T2 lesions
8. Volume of hypointense T1 lesion component (black holes)
9. Proportion of subjects free of disability progression at Weeks 24, 48 and 96.
10. Proportion of subjects with a relapse
11. Time to first confirmed relapse

Change in MSFC and Health Outcomes (MSQoL-54 (inclusive of SF36), FIS), will be analyzed using linear Mixed Models. including results with baseline as a covariate along with region and other covariates if used in the primary analyses.

The analysis of CDI at 12 and 24 weeks will utilize the same approach as that used for CDP. 12 Week Confirmed Disability Improvement (12 Week CDI) is defined as a reduction from the baseline EDSS score of at least 1.0 point (or 0.5 points if the baseline EDSS score was >5.5) that was sustained and confirmed at the next scheduled visit at least 12 weeks after the initial documentation of neurological improvement. Similarly, 24-week Confirmed Disability Improvement (24 Week CDI) requires an initial reduction from baseline EDSS score and a subsequent confirmation of the reduction at all regular scheduled visits for at least 24 Weeks after the initial documentation of neurological worsening

Hospitalization, Steroid Use, and Time Out of Work will be summarized by descriptive statistics as well as frequency and percentage. For Time Out of Work, percentages of missed work hours will be compared between arms using Wilcoxon rank sum tests. For Steroid Use, the number of IRAP confirmed relapses treated with steroid will be analyzed the same way as the primary endpoint.

For analysis of lesion volume related variables (Total volume of Gd enhancing T1 lesions per MRI scan over the treatment period, Volume of T2 lesions, Volume of hypointense T1 lesion component (black holes)) Mixed Model Repeated Measures (MMRM) analyses will be implemented via [REDACTED]

Time to first confirmed relapse is defined as (date of relapse onset – date of randomization + 1) and will be regarded as censored at the end of treatment. The analysis will be similar to the one of time to confirmed disability progression. The proportions of subjects with a relapse and subjects free of disability progression at different time points will be estimated using the Kaplan-Meier method.

[REDACTED]

[REDACTED]

[REDACTED]

[REDACTED]

[REDACTED]

[REDACTED]

[REDACTED]

[REDACTED]

[REDACTED]

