3 STUDY POPULATION

3.1 INCLUSION CRITERIA

Subjects must meet the following inclusion criteria to be eligible for participation in this study:

1. 18-55 age
2. Diagnosis of RMS (McDonald criteria 2010; Appendix C)
3. ≥ 2 relapses in prior 2 years or 1 relapse in the year prior to screening and/or ≥ 1 Gd enhancing lesion
4. Documented MRI of brain with abnormalities consistent with MS
5. Active disease
6. EDSS 0-5.5 (inclusive) at screening
7. B cell counts $\geq 5\%$ of total lymphocytes
8. Neurologic stability ≥ 30 days prior to screening and baseline
9. Female subjects who are not of child-bearing potential, have documented surgical sterilization (see Appendix A), and female subjects of child-bearing potential who have a negative serum pregnancy test at baseline. Female subjects of child-bearing potential (see Appendix A), and all male partners must consent to use a medically/clinically acceptable method of contraception throughout the treatment period and for 20 weeks after the cessation of active treatment. Female subjects of child-bearing potential (see Appendix A) must agree to undertake urine pregnancy tests every 4 weeks during active treatment and the follow up period.
10. Fertile male subjects participating in the study who are sexually active with women of child bearing potential, must agree to use a condom during the treatment period and for an additional 20 weeks after cessation of active treatment. Agree to use an accelerated elimination procedure after the last dose of study medications or early termination from the study (see Section 6.10.1)
11. Willingness and ability to comply with trial and follow-up procedures, give written consent

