6.3.2 DISABILITY EVALUATION

Disability Progression

The method of disability progression calculation will be different than that of the relapsed confirmation. The EDSS score will be used to assess disability progression. EDSS assessment will be performed by the Examining Neurologist. The Examining Neurologist must not share the EDSS score with the Treating Neurologist. The EDSS assessment for disability progression will be performed at screening and on Week 1 Day 1 (prior to randomization) and Weeks 12, 24, 36, 48, 60, 72, 84 and 96. Disability progression is a post hoc analysis only and will not be calculated by the Evaluating Neurologist or other study staff.

The EDSS is based on a standard neurological examination, incorporating the following function systems (pyramidal, cerebellar, brainstem, sensory, bowel and bladder, visual, and cerebral) and ambulation rated and scores as function system scores (FS). Each FS score is an ordinal clinical rating scale ranging from 0 to 5 or 6. These ratings are then used in conjunction with observations and information concerning ambulation and used of assistive devices to determine the EDSS score. The EDSS is a disability scale that ranges in 0.5-point steps from 0 (normal) to 10 (death).

The randomization process must ensure that the baseline EDSS is assessed for the subject by the Examining Neurologist and is documented before treatment is assigned.

Disability progression can only be assessed from the EDSS scores performed at baseline and on Week 1 Day 1 and Weeks 12, 24, 36, 48, 60, 72, 84 and 96.

Disability progression is defined as an increase of ≥ 1.0 point from the baseline EDSS score that is not attributable to another etiology (e.g., fever, concurrent illness, or concomitant medication) when the baseline score is 5.5 or less, and ≥ 0.5 when the baseline score is above 5.5.

Disability progression is considered confirmed when the increase in the EDSS score is confirmed at regularly scheduled visits at least 12 or 24 weeks after the initial documentation of neurological worsening.

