## 2.2.3 Modified Intention-to-Treat (mITT) Population

The modified Intention-to-Treat (mITT) population will consist of all subjects in the ITT population who received at least one dose of study medication and have at least one baseline and post baseline efficacy assessment. The primary efficacy analyses (of primary, secondary and tertiary efficacy endpoints, except MRI related) will be performed based on the mITT population.

The MRI related efficacy analyses will be performed on the subjects in mITT population who have baseline and post-baseline MRI efficacy assessments (mITT-MRI).

Subjects will be analyzed by randomized treatment group.

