#### 2.4.4.2 Disability endpoints

24 week Confirmed Disability Progression (24 Week CDP) is defined as an increase of  $\geq 1.0$  point from the baseline EDSS score that is not attributable to another etiology (e.g., fever, concurrent illness, or concomitant medication – this information will be reflected in the assessments documented by the investigator. In the statistical analysis no further checks are necessary.) when the baseline score is 5.5 or less, and  $\geq 0.5$  when the baseline score is above 5.5. Disability progression is considered confirmed when the increase in the EDSS is confirmed at a regularly scheduled visit at least 24 weeks after the initial documentation of neurological worsening.

12 Week Confirmed Disability Improvement (12 Week CDI) is defined as a reduction from the baseline EDSS score of at least 1.0 point (or 0.5 points if the baseline EDSS score was  $>5.5$ ) that was sustained and confirmed at the next scheduled visit at least 12 weeks after the initial documentation of neurological improvement. Similarly, 24-week Confirmed Disability Improvement (24 Week CDI) requires an initial reduction from baseline EDSS score and a subsequent confirmation of the reduction at all regular scheduled visits for at least 24 Weeks after the initial documentation of neurological worsening.

The analysis of the time to 24-week CDP and CDI at 12 and 24 weeks will utilize the same approach as that used for 12-week CDP (including subject proportions).

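### The 24-week confirmed disability improvement window is anchored on worsening instead of improvement, and CDI proportions include subjects who cannot fall by 1.0 point

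*Protocol*

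**What the plan says.** **Definition.** In protocol 8.9.4, 12-week CDI "is defined as a reduction from the baseline EDSS score of at least 1.0 point", or 0.5 points if baseline is above 5.5. SAP 2.4.4.2 uses the same rule and requires the reduction to be "sustained and confirmed at the next scheduled visit at least 12 weeks after the initial documentation of neurological improvement".

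**24-week version.** The next sentence in each document requires an initial reduction and its later confirmation. Protocol 8.9.4 sets the confirmation "for at least 24 Weeks after the initial documentation of neurological worsening". The SAP repeats this, asking for confirmation of the "reduction at all regular scheduled visits for at least 24 Weeks after the initial documentation of neurological worsening". Neither sentence states how large the initial reduction must be.

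**Who is analysed.** Protocol 3.1 admits "EDSS 0-5.5 (inclusive) at screening". Protocol 6.3.2 describes the EDSS as running upward from 0 in half-point steps. SAP 2.2.3 states: "The primary efficacy analyses (of primary, secondary and tertiary efficacy endpoints, except MRI related) will be performed based on the mITT population". SAP 2.4.4.2 analyses CDI in the same way as 12-week progression (CDP), including subject proportions. SAP 2.4.3.5 censors subjects without an event at their last scheduled EDSS.

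**Status.** Protocol 8.9.2 lists 12- and 24-week CDI among the four prespecified pooled analyses of RMS301 and RMS302 and labels both tertiary. Protocol 8.9.4 tests tertiary endpoints at 0.05 without multiplicity adjustment.

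**The concern.** There are two separate issues.

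1. The 24-week improvement rule opens its confirmation window at a documented worsening. An improvement endpoint has no reason to depend on one, and the 12-week rule in the same paragraph does not. The SAP, which should settle such details, carries the same word. An event definition ought to have a single reading before database lock, so that nothing is left to choose after unblinding.

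2. A subject whose baseline EDSS is below 1.0 cannot fall by 1.0 point, yet counts as a non-improver in the denominator and stays in the risk set until censored. The reported proportion improving therefore mixes how often improvement happens with how many subjects had room to improve.

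**Working it through.** The documents give no expected CDI proportion, event count or power, so there is no figure of theirs to reproduce.

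**Anchor: the rules side by side**

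| Endpoint | Location | Confirmation counted from first documentation of |
|---|---|---|
| 12- and 24-week CDP | Protocol 8.9.2 | worsening |
| 24-week CDP | SAP 2.4.4.2 | worsening |
| 12-week CDI | Protocol 8.9.4, SAP 2.4.4.2 | improvement |
| 24-week CDI | Protocol 8.9.4, SAP 2.4.4.2 | worsening |

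The last row matches the progression rows and not its own 12-week counterpart, which is what a carried-over phrase would produce.

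Take a subject who is 1.0 point below baseline at every scheduled visit from Week 12 to Week 96. Anchored on improvement, the window opens at Week 12, Weeks 24 and 36 confirm it, and the subject has the event. Anchored on worsening, no worsening was documented, the window never opens, and the status is undefined or non-event.

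A toy simulation shows how common this could be. Its inputs are assumptions: 200,000 subjects; baseline drawn evenly from 0, 1.0, 1.5 and so on to 5.5; eight post-baseline visits; at each visit no change with probability 0.70, 0.5 up or down with probability 0.11 each, and 1.0 up or down with probability 0.04 each. Anchored on improvement, 17.6% met 24-week CDI, and 98.9% of those never had an EDSS rise large enough to count as progression. The percentages belong to the model; the point is that improvers need not have worsened.

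**Floor**

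The lowest score is 0, so a fall of 1.0 needs a baseline of at least 1.0. Let f be the share of mITT subjects below 1.0 and p the proportion improving among the rest. Then

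reported proportion = (1 − f) × p.

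The simulation agrees. With 9.1% of subjects at baseline 0, none of those (about 18,000) met CDI, and the overall proportion was 0.909 of that among subjects at 1.0 or above.

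The documents do not give f. Assume 5% to 30%, and for illustration p = 10% on teriflunomide and 16% on ublituximab. Power is for comparing two proportions with 440 per arm: 220 per group in each of two studies, assuming RMS301 is the same size and nobody is lost. In the restricted set there are 440 × (1 − f) per arm. The approximate hazard ratio is ln(1 − p_U) / ln(1 − p_T), using the reported proportions.

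| f | Reported, teri vs ubli | Difference (points) | Risk ratio | Approx. HR | Power, all mITT | Power, baseline ≥ 1.0 |
|---|---|---|---|---|---|---|
| 0 | 10.0% vs 16.0% | 6.0 | 1.60 | 1.655 | 75.5% | 75.5% |
| 5% | 9.5% vs 15.2% | 5.7 | 1.60 | 1.652 | 73.0% | 73.3% |
| 10% | 9.0% vs 14.4% | 5.4 | 1.60 | 1.649 | 70.3% | 71.0% |
| 20% | 8.0% vs 12.8% | 4.8 | 1.60 | 1.643 | 64.6% | 65.9% |
| 30% | 7.0% vs 11.2% | 4.2 | 1.60 | 1.637 | 58.2% | 60.1% |

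Power falls down both columns because fewer subjects can have the event. Removing the others recovers at most about 2 points over this range.

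**The case against.** **On the anchor.** A reader might infer that 24-week CDI cannot be programmed, or that improvers will be misclassified: for example, a subject worse at Week 12 and improved from Week 36 to Week 96 would fail because Week 24 shows no reduction. The documents do not support that. The sentence is tied by 'Similarly' to the 12-week rule, starts from an initial reduction, and asks for confirmation subsequent to it. A visit before the reduction cannot be one of the confirming visits. Misclassification arises only if the last word is applied and the rest of the sentence ignored. The event time is also untouched, because SAP 2.4.3.5 counts it from randomization. All of this stands. It makes the point an erratum, but nothing visible corrects the word in either document.

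**On the floor.** A reader might infer that the treatment comparison is biased, or that the mITT analysis should be replaced. Neither follows. Randomization makes f equal across arms in expectation, the risk ratio cancels (1 − f), and the hazard ratio and power barely move. The difference in proportions does shrink, but the visible text plans proportions with confidence intervals by arm and no between-arm difference. The proportion improving among all mITT subjects is a legitimate prespecified quantity on the same set as CDP, and restricting the set answers a different question. Exclusion 8 in protocol 3.2 also removes subjects with EDSS of 2.0 or less and at least 10 years of disease, which thins the low end, although EDSS 0 with shorter disease remains eligible. What survives is that the absolute proportions cannot be interpreted without knowing f.

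**On completeness.** Parts of the SAP, including section 2.2.5, are redacted, so a restriction there cannot be ruled out. The visible mITT rule contains none for CDI.

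**Conclusion.** The 24-week CDI anchor is wrong as written in both documents and should be corrected. The intended reading can be recovered from context, so the harm is confined to a literal implementation, under which improvers who never worsened would have no window start. How many that would be is not established; the simulation is illustrative only.

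The floor effect is arithmetically certain wherever subjects with baseline EDSS below 1.0 are enrolled, but its size is unknown. Under the assumed f of 5% to 30%, absolute CDI proportions are lowered by the same 5% to 30% in relative terms, with the relative effect and power essentially unchanged. This limits description and does not affect validity.

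Because CDI is tertiary and unadjusted, no confirmatory conclusion depends on either issue.

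**What to change.** 1. In protocol 8.9.4 and SAP 2.4.4.2, replace 'worsening' with 'improvement' in the 24-week CDI sentence, and state that the threshold of 1.0 point (0.5 if baseline is above 5.5) applies at 24 weeks as well.
2. Keep the wording matched in the RMS301 documents, because CDI is analysed on pooled data.
3. Keep the mITT analysis of 12- and 24-week CDI. Beside it, report time to event and proportions in mITT subjects with baseline EDSS of at least 1.0, and give the number below 1.0 by arm so that f is known. Specify this subset for RMS301 too.

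The cost is a wording change in both studies' documents and one additional summary per CDI endpoint. No new data are needed, and the subset loses no possible event. The changes should be made before database lock and unblinding.

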8.9.6 ANTI-DRUG ANTIBODY (ADA) ANALYSIS

Immunogenicity results will be reported based on all subjects in the safety population. The percentage of subjects developing ADA will be summarized. .

9 SAFETY REPORTING AND ANALYSIS

9.1 SAFETY ANALYSES

To evaluate the safety of ublituximab/placebo and teriflunomide/oral placebo, as determined by adverse events (AEs) and serious adverse events (SAEs), including MS worsening.

Safety will be tabulated as described below in the safety section. Tables will summarize the proportion of subjects ever experiencing a particular AE, and in select tables will also include the number of times a particular AE occurs.

Safety evaluations will be based on the incidence, intensity, and type of adverse events, as well as on clinically significant changes in the subject's physical examination, vital signs, and clinical laboratory results. Safety analyses will be performed using the safety population. Safety variables will be tabulated and presented by treatment actually received. Exposure to study treatment and reasons for discontinuation of study treatment will also be tabulated. Must obtain expert evaluations of brain MRI images of subjects with suspected opportunistic CNS infections including PML.

For select laboratory values, box plots of the values over time will be used for displays of these parameters. In the event of higher than expected incidence rates of abnormalities, further exploration of combinations of events, such as Hy's law, will be examined.

9.2 ADVERSE EVENTS

Adverse event (AE) monitoring and reporting is a routine part of every clinical trial.

An adverse event (AE) is any untoward medical occurrence in a subject or clinical investigation subject administered a pharmaceutical product. An AE does not necessarily have to have a causal relationship with this treatment. An adverse event (AE) can therefore be any unfavorable and unintended sign (including an abnormal laboratory finding, for example), symptom, or disease temporarily associated with the use of a medicinal product, whether or not considered related to the medicinal product. This includes any occurrence that is new in onset or aggravated in severity or frequency from the baseline condition.

9.3 ADVERSE EVENT CHARACTERISTICS

The descriptions and grading scales found in the revised NCI Common Terminology Criteria for Adverse Events (CTCAE) version 4.03 will be utilized for AE reporting. All appropriate treatment areas should have access to a copy of the CTCAE version 4.03. A copy of the CTCAE version 4.03 can be downloaded from the following web site http://ctep.cancer.gov/protocolDevelopment/electronic_applications/ctc.htm.

The NCI Common Terminology Criteria for Adverse Events (CTCAE) v4.03 is to be used for the grading of severity of symptoms and abnormal findings. For adverse events not covered by the NCI-CTCAE Version 4.03 grading system, the following definitions will be used:

- **Grade 1:** Mild; asymptomatic or mild symptoms; clinical or diagnostic observations only; intervention not indicated.
- **Grade 2:** Moderate; minimal, local or non-invasive intervention indicated.
- **Grade 3:** Severe or medically significant but not immediately life-threatening; hospitalization or prolongation of hospitalization indicated.
- **Grade 4:** Life-threatening consequences; urgent intervention indicated.
- **Grade 5:** Death related to AE.

9.4 ADVERSE EVENT EXPECTEDNESS

AEs can be 'Unexpected' or 'Expected' for expedited reporting purposes only. Expected AEs are those listed in the Investigator Brochures for either ublituximab or teriflunomide.

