7.1.1.1 VERY COMMON ($\geq 10\%$)

- **Gastrointestinal Disorders:** Diarrhea, Nausea
- **Hepatic Disorders:** Elevated Alanine Aminotransferase Level
- **Nervous System Disorders:** Headache
- **Skin and Subcutaneous Tissue Disorders:** Hair Loss

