7.2.1.2 COMMON (≥ 2 - $< 10\%$)

- **Blood and Lymphatic System Disorders:** Anemia, Pancytopenia
- **Musculoskeletal and Connective Tissue Disorders:** Muscular Weakness
- **Nervous System Disorders:** Dysgeusia
- **Vascular Disorders:** Hypertension
- **Gastrointestinal Disorders:** Diarrhea, Nausea, Abdominal Pain, Oral Pruritus
- **General Disorders and Administration Site Conditions:** Fatigue, Asthenia, Chills, Edema Peripheral, Pain
- **Hepatobiliary Disorders:** Cytolytic Hepatitis
- **Infection and Infestations:** Herpes Zoster
- **Investigations:** Aspartate Aminotransferase Increased, Blood Bilirubin Increased, Gamma-glutamyltransferase Increased
- **Respiratory, Thoracic and Mediastinal Disorders:** Throat Irritation, Throat Tightness
- **Skin and Subcutaneous Tissue Disorders:** Pruritus, Hyperhidrosis

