9.6 ADVERSE EVENTS / SERIOUS ADVERSE EVENT CAUSALITY ASSESSMENT

The Investigator must also assess the relationship of any adverse event to the use of study drug, (whether none, one, or all) based on available information, using the following guidelines:

1. **Not Related:** Clear-cut temporal and/or mechanistic relation to a cause other than the study drug.
2. **Doubtful:** There is no reasonable possibility that the event is related to the study medications but a definite cause cannot be ascertained.
3. **Possible:** There is still a reasonable possibility that the cause of the event was the study medications but there exists a more likely cause of the event such as complications of progressive disease.
4. **Probable:** The most likely cause of the event is the study medications but other causes cannot be completely excluded.
5. **Definite:** Clear cut temporal and/or mechanistic relation to the study medications. All other causes have been eliminated. Events classified as definite will often be confirmed

by documenting resolution on discontinuation of the study medications and recurrence upon resumption.

In the summary of drug related AEs, “Not Related” and “Doubtful” will be considered as “Not Drug Related” and “Possible”, “Probable”, and “Definite” will be considered as “Drug Related.” In the event that causality is missing for an AE, it will be considered as “Drug Related.”

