9.7 SERIOUS ADVERSE EVENTS

9.7.1 DEFINITIONS OF SERIOUS ADVERSE EVENTS

The definitions of serious adverse events (SAEs) are given below. The Principal Investigator is responsible for ensuring that all staff involved in the trial are familiar with the content of this section.

An SAE or reaction is defined as any untoward medical occurrence that:

- Results in death, is immediately life-threatening,
- Requires in-patient hospitalization or prolongation of existing hospitalization,
- Results in persistent or significant disability/incapacity, and/or
- Causes a congenital anomaly/birth defect.

Medical and scientific judgment should be exercised in deciding whether expedited reporting is appropriate in other situations, such as important medical events that may not be immediately life-threatening or result in death or hospitalization, but may jeopardize the subject or may require intervention to prevent one of the other outcomes listed in the previous definition. These should also usually be considered serious. Examples of such events are intensive treatment in an emergency room or at home for allergic bronchospasm; blood dyscrasias or convulsions that do not result in hospitalization; or development of drug dependency or drug abuse.

A SUSAR is defined as a suspected unexpected SAE, and SUSAR reporting is encompassed within SAE reporting guidelines as defined in this section.

Treatment within or admission to the following facilities is not considered to meet the criteria of "in-patient hospitalization" (although if any other SAE criteria are met, the event must still be treated as an SAE and immediately reported):

- Emergency Department or Emergency Room
- Out-patient or same-day surgery units
- Observation or short-stay unit
- Rehabilitation facility
- Hospice or skilled nursing facility
- Nursing homes, Custodial care or Respite care facility

Hospitalization due to MS relapse does not need to be reported to the Sponsor as an SAE if the Treating Neurologist medically confirms the relapse. The subsequent IRAP adjudication will not impact the reporting status of the SAE.

Events related to underlying MS disease (i.e., MS progression) also do not require reporting as an SAE.

Hospitalization during the trial for a pre-planned surgical or medical procedure (one which was planned prior to entry in the trial), does not require reporting as a serious adverse event to the Sponsor.

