9.8 SPONSOR SAE REPORTING REQUIREMENTS

Sponsor is responsible for reporting relevant SAEs to the Competent Authority, other applicable Regulatory Authorities, and participating investigators, in accordance with ICH guidelines, FDA regulations, and/or local regulatory requirements.

Sponsor is responsible for reporting related, unexpected fatal or life-threatening events associated with the use of the trial drugs to the regulatory agencies and competent authorities via telephone or fax within 7 calendar days after being notified of the event. The Sponsor will report all related, unexpected SAEs including non-death/non-life-threatening SAEs associated with the use of the trial medications to the applicable Regulatory Authorities, investigators, and central IRBs or EC by a written safety report within 15 calendar days of notification. Investigators using local IRBs or EC are responsible for sending written safety reports for these events to their IRBs or EC within 15 calendar days or accordingly to the timelines outlined in the policies of the responsible IRB or EC.

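### Section 9.4 pools the two brochures when it defines an expected AE, so a serious reaction unlisted for the suspected drug but listed for the other would not trigger the sponsor's 7- or 15-day report

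*Protocol*

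**What the plan says.** Protocol Section 9.4 has two sentences. The first limits the purpose of the label: "AEs can be 'Unexpected' or 'Expected' for expedited reporting purposes only". The second defines it: "Expected AEs are those listed in the Investigator Brochures for either ublituximab or teriflunomide".

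The label is then used in two places. Section 9.7.1 states "A SUSAR is defined as a suspected unexpected SAE". Section 9.8 sets the sponsor's clocks. For seven calendar days: "Sponsor is responsible for reporting related, unexpected fatal or life-threatening events associated with the use of the trial drugs". For fifteen: "The Sponsor will report all related, unexpected SAEs including non-death/non-life-threatening SAEs associated with the use of the trial medications". The 7-day report goes to the authorities. The 15-day report goes to authorities, investigators and central IRBs or ECs.

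Causality, by contrast, is assessed by drug. Section 9.6 reads "The Investigator must also assess the relationship of any adverse event to the use of study drug, (whether none, one, or all", and Section 9.6.1 names the infusion and the tablets as separate possible causes. SAP Section 2.4.5.1 summarises related TEAEs by relationship to IV and/or oral treatment.

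**The concern.** Ublituximab and teriflunomide are different kinds of drug (an anti-CD20 antibody and a pyrimidine synthesis inhibitor), each with its own brochure. A reaction familiar for one may be new for the other. Expectedness exists to separate what is already documented for the suspected product from what is new, and only the new is expedited. If a listing for either drug is enough, knowledge about drug B removes the expedited report for a reaction attributed to drug A.

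At stake is prompt notice from the sponsor to authorities, to investigators at other sites and to central IRBs or ECs about a reaction new for the suspected product. No endpoint, analysis population or AE table is involved, because Section 9.4 confines the label to expedited reporting.

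**Working it through.** No arithmetic applies. The check traces one event through the sections, then looks for text that would change the result.

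**Trace.** Take a serious event that the investigator attributes to drug A only, absent from brochure A and present in brochure B.

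1. Section 9.6: related to A. The one-drug option exists, so this is a permitted record.
2. Section 9.4: listed in one of the two brochures, so expected.
3. Section 9.7.1: not unexpected, so not a SUSAR.
4. Section 9.8: related but not unexpected, so neither the 7-day nor the 15-day trigger is met.

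**Comparison of rules for a serious event attributed to A alone.**

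| Listed for A | Listed for B | Section 9.4 as written | Judged against A's brochure |
|---|---|---|---|
| yes | yes | expected | expected |
| yes | no | expected | expected |
| no | yes | **expected** | **unexpected** |
| no | no | unexpected | unexpected |

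The rules differ only in the third row. That row exists in both directions: A can be ublituximab or teriflunomide.

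**Is there correcting text?** Neither document ties expectedness to the suspected product. Section 9.8 opens with a general duty to report relevant SAEs in line with ICH, FDA and local requirements, but gives no rule for expectedness. Section 9.7.2 refers to a Safety Monitoring Plan, which is not among the documents.

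**Can the third row be non-empty?** The protocol's own risk lists (Sections 7.1.1 and 7.2.1) differ. Pancytopenia and "Cytolytic Hepatitis" appear only for ublituximab; hair loss and "Elevated Alanine Aminotransferase Level" appear only for teriflunomide. If the brochures matched these lists, serious pancytopenia attributed to the tablets would be classed as expected because of the ublituximab list. This is an illustration only. Section 9.4 refers to the brochures, and Sections 7.1.1 and 7.2.1 say that the brochures carry the complete lists, regardless of causality. A term absent from a protocol list may still be in that drug's brochure.

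**What does not pass through Section 9.4?** Under Section 9.7.2 every SAE goes to the sponsor within 24 hours whatever its causality, and investigators report SAEs to their own IRB/EC under that body's policies; expectedness is a condition for neither. Under Section 4.2.1 the DSMB receives unblinded safety data by treatment group.

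**The case against.** The strongest reply is that this is loose wording with little practical effect. It has four parts.

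*Either may have been meant as the respective drug.* Possible, but the sentence does not say so, and its plain reading is the pooled one. If the respective drug was meant, the correction merely states the intent.

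*Section 9.8 already binds the sponsor to ICH, FDA and local requirements.* This carries weight. The clause may lead the sponsor to a product-specific test in practice, and the unseen Safety Monitoring Plan may already contain one. It does not correct Section 9.4; it leaves safety staff with a specific definition and a general duty that may point different ways.

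*Other routes remain open.* This stands. A reader might infer that such an event would stay hidden from ethics committees, or wait for periodic review. The documents do not support that: the 24-hour report to the sponsor, the investigator's report to the IRB/EC and DSMB review all continue. What Section 9.4 can stop is the sponsor's onward expedited report. DSMB review does not replace it, since the board advises the sponsor and its guaranteed meeting frequency is at least annual.

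*A pooled rule is practical under the blind.* Every subject receives both an infusion and tablets, one of them placebo, so a blinded attribution may fall on a placebo. This is a real difficulty, and any replacement must deal with it. But the protocol already asks for causality by drug while blinded, so the pooled rule discards information that is collected anyway.

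**Conclusion.** The point holds as a defect of wording with a definite consequence. Followed literally, Sections 9.4, 9.7.1 and 9.8 together remove the sponsor's 7- and 15-day reports for one class of event: serious, attributed to one drug, unlisted for that drug, listed for the other. It rests on the literal reading of either and on the absence of a product-specific rule elsewhere, which can be confirmed only for the documents at hand.

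The size cannot be given. A reader might be tempted to count the terms that appear on only one of the lists in Sections 7.1.1 and 7.2.1 and treat each as a lost report. Those lists are excerpts and the brochures were not seen, so no affected term is established. The illustration is also clearer in one direction. Pancytopenia would concern the comparator tablets. For a reaction new for ublituximab, the teriflunomide-only terms are elevated ALT, hair loss, joint pain and numbness, and the ublituximab list already contains related liver terms. Nor do the documents show that any report has been or would be missed; they show only that the written rule would not require it.

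The wording should be corrected, because the rule decides what is reported promptly and the correction is short.

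**What to change.** Reword Section 9.4 so that expectedness is judged for each product to which the event is attributed: against the ublituximab brochure for the IV component and against the teriflunomide brochure for the oral component.

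Add a rule for events attributed to both components, or not separable while treatment is blinded. One workable choice is to class such an event as unexpected if it is unlisted for either product. State also who breaks the blind for an individual case and how the study team is kept from the result. Make the SUSAR definition in Section 9.7.1 and the triggers in Section 9.8 refer to this rule, and check that the Safety Monitoring Plan agrees.

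No new data item appears necessary, since relationship to IV and oral treatment is already planned. The cost is an amendment to the wording of the protocol and safety plan, plus some additional expedited reports and associated individual unblindings. For events attributed to both products the example rule is strict, because it requires a listing in both brochures where Section 9.4 now accepts one. The extra volume cannot be estimated without the brochures, and the sponsor should gauge it before fixing that part of the rule.
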